If your research investigates any aspect of COVID-19, please include "COVID19" at the beginning of your Project Title and Short Title

Efficacy of the OrthoApnea NOA® mandibular advancement device in the management of obstructive sleep apnea. Clinical trial and retrospective comparison study.

Short Title Description

Please use a few key words to easily identify your study - this text will be displayed in the Dashboard listing for your study.

Mandibular advancement device for OSA

Anticipated Ending Date of Research Project: 7/31/2023

Maximum number of human subjects (or records/specimens to be reviewed) 50

After approval, will the study be open to enrollment of new subjects or new data/specimen collection? Yes No

PI CONTACT INFORMATION**0 unresolved comment(s)****Principal Investigator (PI) role for E-IRB access**

The PI is the individual holding primary responsibility on the research project with the following permissions on the E-IRB application:

1. Read;
2. write/edit;
3. receive communications; and
4. submit to the IRB (IR, CR, MR, Other Review*).

If research is being submitted to or supported by an extramural funding agency such as NIH, a private foundation or a pharmaceutical/manufacturing company, the PI listed on the grant application or the drug protocol must be listed as PI here.

Please fill in any blank fields with the appropriate contact information (gray shaded fields are not editable). Required fields left blank will be highlighted in pink after you click "Save".

To change home and work addresses, go to [myUK](#) and update using the Employee Self Service (ESS) portal. If name has changed, the individual with the name change will need to submit a '[Name Change Form](#)' to the Human Resources Benefits Office for entering into SAP. The new name will need to be associated with the individual's Link Blue ID in SAP before the change is reflected in E-IRB. Contact the [HR Benefits Office](#) for additional information.

The Principal Investigator's (PI) contact information is filled in automatically based on who logged in to create the application.

If you are not the Principal Investigator, do NOT add yourself as study personnel.

To change the PI contact information on an application in Researcher edit status:

- click "Change Principal Investigator";
- search for the PI's name using the search feature;
- click "Select" by the name of the Principal Investigator, then "Save Contact Information".

You will automatically be added as study personnel with editing permissions to continue editing the application.

Describe the characteristics of the subject population, including age range, gender, ethnic background and health status. Identify the criteria for inclusion and exclusion.

Provide the following information:

- A description of the subject selection criteria and rationale for selection in terms of the scientific objectives and proposed study design;
- A compelling rationale for proposed exclusion of any sex/gender or racial/ethnic group;
- Justification for the inclusion of vulnerable groups such as children, prisoners, adults with impaired consent capacity, or others who may be vulnerable to coercion or undue influence.

Please consider these resources:

[NIH Diversity Policy](#)

[FDA Diversity Guidance](#)

For the prospective section, based on the effect sizes of the mandibular advancement device (MAD) based on past meta-analyses, we conducted a GPower which revealed that obtaining a sample size of 45 participants would provide us 80% power to detect the anticipated effects. To compensate for dropout/attrition, we aim to recruit 50 participants.

No specific population will be targeted in terms of sex/gender or racial/ethnic background. The age range considers patients between 18 and 80 y.o. with a diagnosis of obstructive sleep apnea (OSA). Participants will be recruited from the consecutive patients referred to the Orofacial Pain Clinic for the management of OSA with a MAD.

Inclusion criteria:

- Age: >18 and <80 years old.
- No history of previous use of a MAD.
- Diagnosis of OSA by a sleep physician based on a PSG or HSAT (done >12 months before - evaluation date or > 12 months with >10% variation of BMI).
- Upon clinical examination: >8 teeth per arch; range of anteroposterior mandibular mobility >5 mm.
- Informed consent to participate in the study.

Exclusion criteria:

- Patients with concomitant diagnosed sleep disorders (i.e. insomnia, narcolepsy, restless legs syndrome, rapid eye movement sleep behavior disorder).
- History of previous allergic reaction to the appliance material (Polyamide 12).
- Patients using combination therapy for the management of OSA (i.e. PAP therapy or positional therapy).
- Upon clinical examination: periodontal disease (>4 mm on periodontal probing, with bleeding on probing, visual signs of periodontal inflammation); tooth horizontal mobility >1 mm, vertical mobility, and unfavorable crown to root ratio; open cavities, loose or fractured restorations, or patient undergoing restorative dental treatments.
- Exaggerated gag reflex.
- Lack of coordination or dexterity.
- Inadequate English comprehension.

For the retrospective section, the same inclusion and exclusion criteria will be considered when doing the data extraction.

The proposed dates of enrollment are from October/November 2021 to October/November 2022 (12 months since the starting date).

Attachments

Attach Type	File Name
StudyPopulation	Protocol NOA DEVICE 09202021.docx

Indicate the targeted/planned enrollment of the following members of minority groups and their subpopulations. Possible demographic sources: [Census Regional Analyst Edition](#), [Kentucky Race/Ethnic Table](#), [Kentucky Population Data](#).

(Please note: The IRB will expect this information to be reported at Continuation Review time for Pre-2019 FDA-regulated Expedited review and Full review applications):

Participant Demographics				
	Cisgender Man	Cisgender Woman	TGNB/TGE	Unknown/Not Reported
American Indian/Alaskan Native:	0	0		
Asian:	1	1		
Black/African American:	3	3		
Latinx:	1	1		
Native Hawaiian/Pacific Islander:	0	0		
White:	20	20		

American Arab/Middle Eastern/North African:			
Indigenous People Around the World:			
More than One Race:			
Unknown or Not Reported:	0	0	

If unknown, please explain why:

Participants will be recruited from the patients referred to the Orofacial Pain Clinic (College of Dentistry, UK Kentucky Clinic), not targeting any specific population.

Indicate the categories of subjects and controls to be included in the study. You may be required to complete additional forms depending on the subject categories which apply to your research. If the study does not involve direct intervention or direct interaction with subjects, (e.g., record-review research, outcomes registries), do not check populations which the research does not specifically target. For example: a large record review of a diverse population may incidentally include a prisoner or an international citizen, but you should not check those categories if the focus of the study has nothing to do with that status.

Check All That Apply (at least one item must be selected)

ADDITIONAL INFORMATION:

- Children (individuals under age 18)
- Wards of the State (Children)
- Emancipated Minors
- Students
- College of Medicine Students
- UK Medical Center Residents or House Officers
- Impaired Consent Capacity Adults
- Pregnant Women/Neonates/Fetal Material
- Prisoners
- Non-English Speaking (translated long or short form)
- International Citizens
- Normal Volunteers
- Military Personnel and/or DoD Civilian Employees
- Patients
- Appalachian Population

Please visit the [IRB Survival Handbook](#) for more information on:

- Children/Emancipated Minors
- Students as Subjects
- Prisoners
- Impaired Consent Capacity Adults
- Economically or Educationally Disadvantaged Persons

Other Resources:

- UKMC Residents or House Officers [see [requirement of GME](#)]
- [Non-English Speaking](#) [see also the E-IRB Research Description section on this same topic]
- [International Citizens](#) [DoD SOP may apply]
- [Military Personnel and/or DoD Civilian Employees](#)

Assessment of the potential recruitment of subjects with impaired consent capacity (or likelihood):

Check this box if your study does NOT involve direct intervention or direct interaction with subjects (e.g., record-review research, secondary data analysis). If there is no direct intervention/interaction you will not need to answer the impaired consent capacity questions.

Does this study focus on adult subjects with any conditions that present a high *likelihood* of impaired consent capacity or *fluctuations* in consent capacity? (see examples below)

Yes No

If Yes and you are not filing for exemption certification, go to "[Form T](#)", complete the form, and attach it using the button below.

Examples of such conditions include:

- Traumatic brain injury or acquired brain injury
- Severe depressive disorders or Bipolar disorders
- Schizophrenia or other mental disorders that involve serious cognitive disturbances
- Stroke
- Developmental disabilities
- Degenerative dementias
- CNS cancers and other cancers with possible CNS involvement
- Late stage Parkinson's Disease
- Late stage persistent substance dependence
- Ischemic heart disease
- HIV/AIDS
- COPD
- Renal insufficiency
- Diabetes
- Autoimmune or inflammatory disorders
- Chronic non-malignant pain disorders
- Drug effects
- Other acute medical crises

Attachments

INFORMED CONSENT/ASSENT PROCESS/WAIVER**0 unresolved
comment(s)**

For creating your informed consent attachment(s), please download the most up-to-date version listed in "All Templates" under the APPLICATION LINKS menu on the left, and edit to match your research project.

Additional Resources:

- [Informed Consent/Assent Website](#)
- [Waiver of Consent vs. Waiver of Signatures](#)
- [Sample Repository/Registry/Bank Consent Template](#)

Consent/Assent Tips:

- If you have multiple consent documents, be sure to upload each individually (not all in a combined file).
- If another site is serving as the IRB for the project, attach the form as a "Reliance Consent Form" so the document will not receive a UK IRB approval stamp; the reviewing IRB will need to stamp the consent forms.
- Changes to consent documents (e.g., informed consent form, assent form, cover letter, etc...) should be reflected in a 'tracked changes' version and uploaded separately with the Document Type "Highlighted Changes".
- It is very important that only the documents you wish to have approved by the IRB are attached; DELETE OUTDATED FILES – previously *approved* versions will still be available in Protocol History.
- Attachments that are assigned a Document Type to which an IRB approval stamp applies will be considered the version(s) to be used for enrolling subjects once IRB approval has been issued.

Document Types that do NOT get an IRB approval stamp are:

- "Highlighted Changes",
- "Phone Script", and
- "Reliance Consent Form",
- "Sponsor's Sample Consent Form".

How to Get the Section Check Mark

1. You must:
 - a) provide a response in the text box below describing how investigators will obtain consent/assent, and
 - b) check the box for at least one of the consent items and/or check mark one of the waivers
2. If applicable attach each corresponding document(s) **as a PDF**.
3. If you no longer need a consent document approved (e.g., closed to enrollment), or, the consent document submitted does not need a stamp for enrolling subjects (e.g., umbrella study, or sub-study), only select "Stamped Consent Doc(s) Not Needed".
4. After making your selection(s) be sure to scroll to the bottom of this section and **SAVE** your work!

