At the device delivery appointment, we will fabricate an aligner for the patient to wear for 10 minutes each morning after waking and removing the OrthoApnea NOA® oral appliance. The morning aligner (TAP® AM Aligner) is a record of the patient's habitual bite (the way the teeth come together normally) that will reposition their mandible back into its normal position. It is part of the standard of care for patients undergoing mandibular advancement (MAD) therapy. The aligner is constructed from a thermoplastic material that, when heated, can be molded by hand onto the upper or lower teeth. Once the thermoplastic material is molded around the teeth, they will be instructed to bite down while it is still soft. This will create indentations for the opposing teeth and allow them to be set at their 'normal' and proper biting position. After the molded thermoplastic material has hardened at normal temperature, it is removed from the mouth and trimmed, if needed.

Follow up sessions will be scheduled every two weeks until maximum therapeutic benefit is achieved. At each follow up visit patients will be asked to fill out a questionnaire and further advancement of the MAD will be determined by changes in patients' symptoms and Epworth Sleepiness Scale (ESS). Measures of successful management include: ESS < 10, and >70% reduction or absence of snoring, observed apneic events, and daytime fatigue, to be assessed via questionnaire using a numerical rating scale (NRS). Once the patient has obtained successful management of symptoms, 80% of maximum protrusive or is unable to tolerate the advancement, a home sleep apnea test (Alice NightOne, Phillips Respironics®) will be provided to the patient to perform one night while wearing the appliance to determine the efficacy of the MAD. We will verbally instruct the patient how to operate the machine, and a printed copy of the manufacturer protocol for patients will be provided. Additionally, we will provide our contact number if any question arise. An appointment will be scheduled in the following 2-3 days to return the machine, and to further advance the appliance if needed. Sleep parameters including: AHI, RDI, minimum and average oxygen saturation will be extracted from the initial PSG, and by a trained technician from the final home sleep apnea test, which will be scored following the American Academy of Sleep Medicine Scoring Manual.

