The efficacy of the appliance for the management of OSA will be established based on two criteria. Criterion I: > 50% reduction of AHI/RDI. Criterion II: AHI/RDI < 5 events/hour or <15 events/hour with a significant reduction of OSA associates symptoms as defined before. Therapeutic failure will be established when at 100% of advancement of the device, there is less than 50% of reduction of the AHI/RDI with a residual AHI/RDI >5 events/hour with OSA associates symptoms.

If the criteria for success is reached, the participation of the patient in the present study will be ended. The subject will be offered to continue with standard of care in the OFPC for future follow-ups, and a report will be provided and sent to the treating sleep physician. The subject will be allowed to keep the appliance after the study is completed. If participants do not reach a successful management of OSA at 100% of advancement, they will be referred back to their referring sleep physician to consider another treatment option.

The participation in this research will last between seven to sixteen weeks depending on the time for each patient's individual improvement. The initial visit will last 45-60 minutes, and the follow-up sessions will take about 30-45 minutes. After participation in the study is completed, the participants will be allowed to keep the MAD and all the accessories provided by the manufacturer

RETROSPECTIVE SECTION:

Archival data will be extracted from records of patients that started MAD therapy for OSA at the Orofacial Pain Clinic (University of Kentucky) between 01/01/2010 and 08/17/2021. An active study involving MAD therapy outcomes (protocol #46643; same PI, [name] [name]) includes a consent form for the retrospective participants to collect retrospective data and future use of that data in future research projects. The data collection process of the previous study is being conducted using RED Cap (CCTS - University of Kentucky), and through that software, we intend to obtain a report to identify subjects that started MAD therapy and had a second sleep study performed to assess the effectiveness of the MAD. Data regarding demographic characteristics (age, gender, BMI and OSA

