If this study will use de-identified data from another source, describe what measures will be taken to ensure that subject identifiers are not given to the investigator.

If applicable, describe procedures for sharing data/specimens with collaborators not affiliated with UK.

For additional considerations:

[Return of Research Results or Incidental Research Findings](#)

[HIPAA policies](#)

[FERPA policies](#)

[Procedures for Transfer agreements](#)

[Information regarding multi-site studies](#)

[NIH Genomic Data Sharing \(GDS\) Policy](#)

[Digital Data](#)

PROSPECTIVE SECTION: Information will be mostly obtained via questionnaires (see protocol and annex attached). Demographic information and past reports of diagnostic sleep study will be obtained from EPIC.

RETROSPECTIVE SECTION: Archival data will be extracted from records of patients that started MAD therapy for OSA at the Orofacial Pain Clinic (University of Kentucky) between 01/01/2010 and 08/17/2021. An active study involving MAD therapy outcomes (protocol #46643; same PI, [name] [name]) includes a consent form for the retrospective participants to collect retrospective data that allows to use the obtained data in future research projects. The data collection process of the previous study is being conducted using RED Cap (CCTS - University of Kentucky), and through that software, we pretend to obtain a report to identify subjects that started MAD therapy and that had a second sleep study performed to assess the effectiveness of the MAD. Data

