Active contact with the participants for recruitment, scheduling and clinical sessions, will be carried only by [name] [name], [name] [name] and/or [name] [name]. All the information will be collected via paper questionnaires and forms, and then transferred to an Excel spreadsheet (password protected) that will be stored in a desktop computer (Kentucky Clinic room E214; UK Healthcare system; J066143), to which initially only [name] [name] will have access. In the spreadsheet, the patients will be identified with consecutive numbers (NOA1-NOA50) and their dates of birth. After the recruitment period, the statistician ([name]), [name] [name] and [name] [name] will have access to the deidentified spreadsheet. All the paper questionnaires and forms will be stored (for back up and data verification if needed) in a key locked locker (at Orofacial Pain Clinic, UK Kentucky Clinic, Room E214). Data will be retained for 6 years after study closure and deleted using UK Policy(s) A13-050 and A05-055, under the responsibility of the primary investigator ([name] [name]). A back-up of the data will be performed every week using a flash drive (Endpoint Encryption) that will be stored in a key locked locker at the OFPC (access only by [name] [name]; Kentucky Clinic room E214).

UK IRB policies state that IRB-related research records must be retained for a minimum of 6 years after study closure. Do you confirm that you will retain all IRB-related records for a minimum of 6 years after study closure?

Yes No

[Back to Top](#)

Payment

Describe the incentives (monetary or other) being offered to subjects for their participation. If monetary compensation is offered, indicate the amount and describe the terms and schedule of payment. Please review [this guidance](#) for more information on payments to subjects, including restrictions and expectations.

No monetary payment will be offered. The device and the confirmatory sleep study will be provided with no cost for the participants.

Costs to Subjects

Include a list of services and/or tests that will not be paid for by the sponsor and/or the study (e.g., MRI, HIV). Keep in mind that a subject will not know what is "standard" – and thus not covered by the sponsor/study – unless you tell them.

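### The age rule for the qualifying sleep study is defective as written: both limbs require a study over 12 months old, and that report is the only untreated AHI/RDI baseline described

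*Combined protocol and SAP*

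**What the plan says.** The inclusion criteria in the study-population section require OSA diagnosed by a sleep physician from a PSG or HSAT, with this timing condition: "done >12 months before - evaluation date or > 12 months with >10% variation of BMI". The evaluation date is not defined there. For the retrospective section, "the same inclusion and exclusion criteria will be considered when doing the data extraction".

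The source of the baseline is given in three places:
- Records, Privacy, and Confidentiality: "Demographic information and past reports of diagnostic sleep study will be obtained from EPIC".
- Research Procedures and Data Collection & Research Materials: AHI, RDI and oxygen saturation "will be extracted from the initial PSG, and by a trained technician from the final home sleep apnea test". The final test is one night with the appliance in place.
- Payment: "The device and the confirmatory sleep study will be provided with no cost for the participants". No other sleep test supplied by the study is described.

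Research Procedures then uses the baseline twice. Success can be met by "Criterion I: > 50% reduction of AHI/RDI". Failure means that, with the device fully advanced, "there is less than 50% of reduction of the AHI/RDI with a residual AHI/RDI >5 events/hour", together with symptoms. Study Design describes the prospective part as uncontrolled. Statistical Methods plans paired t-tests before and after treatment without naming AHI or RDI.

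**The concern.** An eligibility rule with two alternatives should admit someone under the second who would not qualify under the first. Here the second alternative repeats the age condition of the first and adds a restriction, so it admits nobody new. The BMI clause was presumably meant to do something, and as written it does nothing. The literal result is also odd: recent studies are shut out, and old ones are let in without limit.

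This is more than untidy drafting because of what the line controls. With no concurrent control and no untreated repeat study, each patient's percentage reduction is measured against one past report. The timing rule is the only stated control on how old that report may be. If a reader cannot tell what the rule was, the reader cannot tell who was eligible or how far apart the two AHI/RDI values were.

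**Working it through.** **1. The rule as written.** Let A = study more than 12 months old and B = BMI change over 10%. The line reads A or (A and B), which equals A.

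| Study age | BMI change | Limb 1 alone | Full rule |
|---|---|---|---|
| up to 12 months | up to 10% | out | out |
| up to 12 months | over 10% | out | out |
| over 12 months | up to 10% | in | in |
| over 12 months | over 10% | in | in |

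The BMI clause changes 0 of 4 decisions. Reading each sign as greater than or equal to would not alter this.

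**2. Can the intended rule be recovered?** The line has three signs (first age, second age, BMI), giving 2 × 2 × 2 = 8 patterns. The columns are recent/stable BMI, recent/changed, older/stable and older/changed.

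| Signs reversed | Rec/stable | Rec/changed | Old/stable | Old/changed |
|---|---|---|---|---|
| none | out | out | in | in |
| BMI | out | out | in | in |
| first age | in | in | out | in |
| second age | out | in | in | in |
| first age and BMI | in | in | in | out |
| second age and BMI | in | out | in | in |
| both ages | in | in | out | out |
| all three | in | in | out | out |

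The BMI clause acts only when the two age signs differ. The eight patterns give six different eligible groups, and every patient type is in under some and out under others. At least one two-sign pattern (first age and BMI) forms a coherent rule. None is proposed here; the table shows only that the text does not identify one.

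**3. Is there another untreated AHI/RDI value?** None is described. Baseline values come from past diagnostic reports, and the study's own test is done on the device. Subject Recruitment Methods recalls patients evaluated within the last 3 years and gives them a new evaluation appointment, but no new untreated study is described for them. The Epworth, symptom and PSQI questionnaires do have baselines at entry, so the gap concerns the sleep-study parameters.

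**4. Interval under the literal rule.** Research Procedures says: "The participation in this research will last between seven to sixteen weeks". Assume that participation starts at the evaluation, that the final test falls near its end, and that a month is 365.25/12 = 30.44 days.
- 7 weeks = 49 days = 1.6 months, so the interval exceeds about 12 + 1.6 = 13.6 months.
- 16 weeks = 112 days = 3.7 months, so the interval exceeds about 12 + 3.7 = 15.7 months.

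There is no upper limit. These figures apply only if the literal rule was the one used.

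**5. How Criterion I depends on the report.** It is met when the final value is below 0.5 × baseline. Each 1 event/hour by which the old report differs from the untreated value at entry therefore moves the cut-off by 0.5 events/hour.

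As an illustration, let x be the true device reduction and r the untreated value at entry divided by the value on the report. Then apparent reduction = 1 − (1 − x) × r. The documents give no r, so 0.7 to 1.3 is an assumed range.
- x = 40%: apparent 58% at r = 0.7, 52% at r = 0.8, 28% at r = 1.2, 22% at r = 1.3.
- x = 60%: apparent 72% at r = 0.7, 48% at r = 1.3.

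Misclassification could go either way.

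**The case against.** The strongest reply is that this is a slip of the pen and that clinic staff applied a sensible rule. A slip is likely, but that does not settle the matter. Reversing different signs gives different groups, and no supplied section says which applied. A sign reversed when the PDF was read is also unlikely, because the less-than sign survives in the age limit of the same list. One limit stands: the study-population section lists an attached protocol file that was not among the supplied documents, and it may state the rule correctly.

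A second reply is that no harm to the result is shown. That also stands. A reader might infer that enrolled patients all had stale baselines, or that the success proportion is inflated. The documents support neither: they do not show that the literal rule was used, and they give no information on how untreated AHI/RDI changed.

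A third reply is that the reach is narrow, and much of this stands:
- Criterion II applies AHI/RDI cut-offs to the final test alone.
- A reader might infer that the advancement percentage in Aim 1.2 is contaminated. Statistical Methods restricts that aim to patients who succeeded but does not say under which criterion, so any carry-over is conditional.
- A reader might infer a biased comparison with the retrospective devices. The same line applies to those records, so any ageing of baselines may be partly shared. Statistical Methods describes the two groups and specifies no test between them.
- A reader might infer that AHI could be set against RDI. Both indices are extracted before and after, so the plan provides for a like-for-like comparison.

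**Conclusion.** The concern holds as a defect in an operative eligibility rule. The BMI condition is without effect in all four patient types, recent studies are excluded, and older ones are accepted without limit. The rule intended, and the rule applied, cannot be established from the supplied text. The line governs the only untreated AHI/RDI reference described, and hence Criterion I and the failure definition. It also bears on the paired tests, on the assumption that AHI and RDI are among the parameters those tests cover.

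No direction or size of bias is claimed. The 0.5 events/hour relation is exact arithmetic; the figures using r are illustrative; the 13.6 to 15.7 month figures are conditional on the literal rule. The point should be fixed, but it does not by itself invalidate the efficacy result.

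**What to change.** 1. Reconcile the timing line. State the rule intended and the rule actually applied, separately for the prospective and retrospective sections. This review does not say which window is right.
2. Define the evaluation date. If it was the study evaluation visit, including the new appointment for recalled patients, say so.
3. Extract from existing records the date of the baseline study, and BMI at that study and at entry. The listed retrospective variables include BMI without a second time point and no study date; the annexed forms were not supplied and may hold more.
4. Report Criterion I and the paired AHI/RDI results with and without patients outside the reconciled rule, as a sensitivity analysis.
5. As a minor wording point, reconcile the inclusion criterion, which allows a PSG or HSAT, with the extraction text, which names only a PSG.

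Statistical Methods is written in the past tense. If enrolment is complete, the useful steps are to disclose the rule applied and run the sensitivity analysis. The cost is one corrected line and a little extra extraction; no new sleep study is needed. The subgroup outside the rule will be small, so the sensitivity result will be imprecise and should be presented that way.
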